4.2. Patients

Pilot Study

Inclusion Criteria

- 1) Patients (>18 years) with histologically confirmed gynaecological malignancy
- 2) Planned chemotherapy
- 3) Written informed consent
- 4) Expected patient compliance

Exclusion criteria:

- 1) Vomiting (CTCAE 4.03) > Grade 2 (3–5 episodes within 24 hours)
- 2) Nasogastric tube or PEG tube
- 3) Previous platinum-based chemotherapy
- 4) Conditions that impair taste perception (e.g., infections in the oral cavity)

Number of study participants:

A total of 40 patients will be enrolled in the study.

RCT

Inclusion criteria:

- 1) Patients (>18 years) with histologically confirmed ovarian cancer/tubal cancer/peritoneal cancer
- 2) Age 18–70 years
- 3) Non-smoker for at least 12 months
- 4) Completed chemotherapy with platinum and taxane
- 5) Written informed consent
- 6) Phantogeusia confirmed through patient interview
- 7) Expected patient compliance

Exclusion criteria:

- 1) Planned or ongoing treatment with a PARP inhibitor
- 2) Known intolerance to HED
- 3) Nausea and vomiting (CTCAE 4.03) > Grade 2 (3–5 episodes within 24 hours)
- 4) Nasogastric tube or PEG tube
- 5) Progressive tumour disease during adjuvant chemotherapy
- 6) Conditions that interfere with taste perception (e.g., infections in the oral cavity)
- 7) General taste disturbance verified by baseline tests

Number of study patients:

A total of 32 patients will be enrolled in the study (active treatment group: 16 patients, placebo group: 16 patients).

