4.5. Timeline

Pilot study

Recruitment	Months 1–12
Analysis	Months 12–15
Total	15 months

RCT

Study planning	Months 1–6
Recruitment	Months 7–30
Analysis	Months 30–36
Total	36 months

B) Statistical Section

1. Sample Size

Forty patients will be recruited for the pilot study. This study is intended to provide a descriptive analysis of taste changes during chemotherapy and to validate the tests used for the double-blind, randomized, placebo-controlled study planned afterwards. The double-blind, randomized, placebo-controlled study will include 32 female patients. Based on current studies [3], the prevalence of bitter phantogeusia is approximately 30–78%. An HED mouthwash leads to a 30% reduction in bitter perception (standard deviation 10%) [7], which describes the expected effect size. The primary endpoint is defined as “comparison of the bitter perception triggered by 500 ppm caffeine from week 1 to week 3 between the study group (HED mouthwash) and the control group (water mouthwash).” The patient rates bitterness perception on a continuous scale from 0 to 10. The study endpoint is therefore a continuous variable. The data from week 1 and week 3 will be analysed using a paired t-test to compare the intervention group with the control group. Taking into account a 20% dropout rate, a 90% power level, and a significance level of 1%, this results in a sample size of 32 patients. These will be randomized 1:1, resulting in a group size of 16 patients each. Approximately 77% of patients experience bitter phantosmia following platinum-based combination chemotherapy. Therefore, approximately 40 patients will need to be screened.

2. Randomization

Randomization is performed online using the randomization program of the Medical University of Vienna (<https://www.meduniwien.ac.at/randomizer/web/login.php>). The complete randomization list is provided to [name], MSc, a staff member of the Institute of Physiological Chemistry. Study medication is packaged and coded, with coding performed exclusively by [name]. The coded, randomized study medication is then distributed as needed to the investigators, who administer the study medication to the patients. The investigators and the statistician may not view the randomization list until the study has been completed.

3. Statistical Analysis

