The efficacy of the treatment is defined as a reduction in the perception of bitterness by more than 30% in the treatment group compared to the placebo group. The primary endpoint will be evaluated using a paired t-test.

This will be evaluated in two analyses:

- Intention-to-treat analysis: Inclusion of all patients who used the mouthwash at least once
- Per-protocol analysis: Inclusion of patients who completed the study according to the study protocol

Secondary endpoints are also analysed using intention-to-treat and per-protocol analyses. The collected clinical and pathological data are presented descriptively using absolute values or, depending on the normality of the distribution, using the median (interquartile range) or mean (standard deviation). Metric variables are compared using Student's t-test or the Mann-Whitney U test, depending on normal distribution. Categorical variables are compared using the chi-square test and, if feasible given the number of groups, presented including the odds ratio (95% confidence interval). The study will investigate predictive factors for response to the intervention. These analyses are performed using a multivariate binary logistic regression model. The following variables are included: patient age, number of chemotherapy cycles, patient BMI, bowel resection during the primary surgery, peripheral polyneuropathy during chemotherapy, nausea at the time of study enrolment, and diarrhoea at the time of study enrolment. Version 21.0 of the statistical software SPSS (SPSS, Inc.) is used for the statistical analysis.

Patient data is pseudonymized, documented, and analysed in accordance with current data protection regulations and is not disclosed to third parties. The data is published in anonymized and aggregated form.

C) Ethical and Legal Section

1. Ethical Aspects

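### A seven-variable logistic model in a 32-patient trial, with neither arm nor an arm interaction listed, will be overfitted and cannot show which patients benefit from HED

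*Combined protocol and SAP*

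**What the plan says.** Section B.3 (Statistical Analysis) says the study will look for factors that predict response to the mouthwash, and then: "These analyses are performed using a multivariate binary logistic regression model". The variables to be included are "patient age, number of chemotherapy cycles, patient BMI, bowel resection during the primary surgery, peripheral polyneuropathy during chemotherapy", plus nausea and diarrhoea at enrolment, which makes seven. Neither treatment arm nor an interaction with arm is listed. The section does not mention variable selection or penalisation and does not call the analysis exploratory. It does not say which patients enter the model, at which visit response is judged, or what makes an individual patient a responder.

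The only threshold in B.3 is a group contrast: efficacy means a reduction of more than 30% in the treatment group relative to placebo. Section B.1 (Sample Size) treats the 0 to 10 bitterness rating as continuous.

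On size, Section 4.2 states "A total of 32 patients will be enrolled in the study", and B.1 adds "These will be randomized 1:1, resulting in a group size of 16 patients each". B.1 allows for 20% dropout, and Section 4.1.2 says withdrawals are not replaced. Section C.1.1 expects that some control patients may also improve through a placebo effect.

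**The concern.** There are three difficulties.

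1. **Size.** Seven slopes and an intercept are to be estimated from at most 32 binary outcomes. Such a fit follows chance patterns in the data. Its odds ratios tend to be exaggerated, with very wide intervals.

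2. **Question.** A factor predicts response to HED only if the HED-placebo difference varies with it. Without arm and an arm-by-variable term, the model describes who improves for any reason, including placebo response and recovery after chemotherapy.

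3. **Outcome.** A binary model needs a rule for each patient. With none written down, the cut-off can be chosen after the data are seen, and dichotomising a continuous rating discards information in a very small trial.

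Section C.1.1 says the data may help to plan a larger validation study. Chance findings from this model could therefore influence that trial's eligibility criteria or stratification.

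**Working it through.** **Inputs from the documents.** 32 patients, 16 per arm (4.2, B.1); 20% dropout (B.1); no replacement (4.1.2); seven listed variables (B.3).

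**The plan's own figure.** No sample-size or precision figure is given for this model. The 32 comes from the primary endpoint. The B.1 inputs (30% reduction, SD 10%, alpha 1%, power 90%) give 6 per arm with an exact two-sided two-sample t-test, and 12/0.8 = 15 in total after dropout, so 32 is not reproduced. That is a separate matter; here 32 serves only as the enrolment ceiling.

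**Step 1: events per variable (EPV).** EPV = patients in the smaller outcome group / number of slopes. A 50% response rate is the best case for any given number of patients; 30% is shown as an assumed alternative. The number evaluable after dropout is 32 × 0.8 = 25.6, about 26, or 13 per arm.

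| Patients in the model | EPV at 50% response | EPV at 30% response |
|---|---|---|
| 32, both arms | 16/7 = 2.29 | 9.6/7 = 1.37 |
| 26, both arms (assumed) | 13/7 = 1.86 | 7.8/7 = 1.11 |
| 16, HED arm only (assumed) | 8/7 = 1.14 | 4.8/7 = 0.69 |
| 13, HED arm only (assumed) | 6/7 = 0.86 (whole patients) | 3.9/7 = 0.56 |

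**Step 2: overfitting.** Simulation with 600 datasets per setting, three continuous and four binary predictors (prevalence 35%, assumed), none related to outcome. Among fits without separation, the median apparent AUC was about 0.77 at n = 32 and 0.80 at n = 26. In a second set of runs (binary prevalences 30/50/30/20%, one true odds ratio of 2 per SD, all assumed), estimable fits at n = 26 or 32 gave a median odds ratio of 2.6 to 2.7. The ratio of upper to lower 95% limit was about 10 to 20, and power was 12 to 34%. At n = 140 the same setup gave a median odds ratio of 2.10 to 2.11 and a limit ratio of 2.3 to 2.4.

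**Step 3: separation.** Checked by linear programming, at response rates of 30% and 50%. The second column includes fits that were otherwise inestimable. Ranges cover repeated runs.

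| n | 35% prevalence, null | 30/50/30/20% prevalence |
|---|---|---|
| 32 | 1.5% to 11% | 10% to 22% |
| 26 | 7% to 25% | 18% to 41% |
| 16 (HED arm) | not run | 80% to 82% |
| 13 (HED arm) | 81% to 93% | 93% to 97% |

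**Step 4: does adding terms rescue it?** Adding arm as a main effect gives 8 slopes and EPV of at most 16/8 = 2.0, still with no interaction. Adding arm and all seven interactions gives 15 slopes: 16/15 = 1.07 at n = 32 and 13/15 = 0.87 at n = 26. In simulation 94 to 98% of those fits at n = 32, and 99 to 100% at n = 26, were separated or inestimable.

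**Step 5: precision of the alternative.** Take a binary modifier that splits each arm of 16 into 8 and 8, and let σ be the residual SD of the week-3 rating. The interaction is a contrast of four cell means, so its standard error is σ√(4/8) = 0.71σ. The overall arm difference has σ√(2/16) = 0.35σ. The 95% interval for the interaction is therefore about 2 × 0.71σ = 1.4σ either side: estimable, but wide.

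**The case against.** The strongest reply is that this is a supplementary analysis. It is not among the endpoints in Section 3.3, it cannot change the primary result, and C.1.1 presents the data as helping to plan a larger study. That limits the consequences. It does not answer the point, because B.3 neither labels the model exploratory nor restricts its aim to prognosis.

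Several stronger statements are tempting but not supported:

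- *The output will be dominated by separation.* In a pooled model separation is a minority event under every assumption tried. It dominates only if the HED arm alone is analysed, and the plan does not say that it will be. The rates also depend on prevalences and response rates that the documents do not give.
- *Only 26 patients will be evaluable.* Section 4.1.2 counts withdrawal up to Visit 3 (week 12) and keeps withdrawn patients in the intention-to-treat analysis. If response is judged at week 3, the number could lie anywhere from about 26 to 32.
- *The HED-arm model has more parameters than responders or non-responders.* With 16 patients split 8 and 8, the eight parameters equal each group. With an uneven split the larger group exceeds eight.
- *Spurious predictors will be published as such.* That is a forecast about reporting.

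Penalised logistic regression could also be proposed. It would deal with infinite estimates, but it would supply neither the interaction nor the responder definition.

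**Conclusion.** The plan is wrong as written on this analysis, at a moderate level of importance. Two findings need no simulation: EPV cannot exceed 2.3 for the seven listed variables, and a model without an arm interaction cannot identify predictors of benefit from HED, whichever patients enter it. The absence of a patient-level response definition is likewise plain from B.3.

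The expected result of a pooled fit is overfitting and imprecision. The size of this (apparent AUC of about 0.77 to 0.80 from noise, and a true odds ratio of 2 estimated at 2.6 to 2.7) rests on the assumed predictor distributions and response rates stated above. Pooled separation of roughly 1 to 25% at 35% prevalence, and up to about 40% under the other prevalences, is a secondary problem. Nothing here affects the primary comparison.

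**What to change.** In Section B.3, replace the seven-variable logistic model with a small number of modifiers, for example one or two, named before unblinding. The exact number is a judgement. For each modifier, fit a separate linear model for the continuous week-3 bitterness rating with baseline rating, arm, modifier and arm-by-modifier. Report the interaction estimate with its confidence interval, label it exploratory, and say in advance that it will be imprecise. State the analysis set. Describe the remaining variables without modelling.

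If a binary response is kept for description, define it per patient, with its visit and cut-off, before the data are seen. If a logistic model is kept at all, describe it as prognostic.

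The cost is SAP wording, with no new data or visits. The downside is that fewer factors are examined formally.

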1.1. The Risk-Benefit Ratio

The homoeriodictyol to be administered in this study was published on the FEMA-GRAS (“generally recognized as safe”) list 22 by the FEXPAN expert panel of the Flavor and Extracts Manufacturers Association (FEMA) in the United States and has thus been deemed generally safe. Substances published on the GRAS list do not require further approval from the Food and Drug Administration (FDA) to be authorized for the market. NaHED (FL. - Number 16.083) has also been included in the EU’s positive list of permitted flavourings (Implementing Regulation No. 872/2012, Official Journal of the European Union, L 267/1) and is provided for this study by Symrise AG, Holzminden, Germany, in the specification required for use as a flavouring.

There are no risks for study participants, and no further examinations or interviews are required. All participants who complete the study will receive compensation for their time and effort in the amount of 130.00 euros. A portion of the compensation will be paid to the participants per visit (visit 1: 50 euros, visit 2: 30 euros, visit 3: 50 euros). For participants in the HED group, a benefit in the form of a reduction in the perception of bitterness is expected. In addition, a partial reduction in the perception of bitterness may also occur in the control group due to the placebo effect. The collected data can be used to facilitate the planning of a further, larger validation study to precisely evaluate the efficacy of HED in chemotherapy-induced bitter phantogeusia.

2. Legal Aspects

